## 7.0 Recruitment Methods:

### 7.1 Select the methods used to recruit individuals.

 Email	 Screening of the Electronic Medical Record (EMR)
 Face to face	 Social media
 Flyers	 SONA System
 In person presentations	 TV, Radio, Print
 Online advertisements	 Other – please explain: Click or tap here to enter text.
 Phone calls	

### 7.2 Explain the recruitment process. Describe how potential subjects will be identified, where recruitment will take place, when recruitment will occur, and the methods that will be used to recruit individuals.

Participants will be recruited under the direction of the PI. PI will oversee participant screening and recruitment. The study team will hand out study flyers/brochures to potential study participants, and those patients who contact the study team for more information about the study will be approached by study investigators or trained study personnel for further determination of eligibility screening requirements and informed consent in-person at a scheduled baseline visit. Coordinators will also recruit through the collaboration with the UA Department of Orthopedic Surgery (Department Chair: [name]) as a study team.

Patients will be identified as potential subjects by a co-investigator on the study team during consultation for standard of care treatment of their knee pain. The study opportunity will be initiated by the treating provider. Only those patients that have expressed interest in the study and have agreed to be contacted will be approached by a study team member through phone, email, or in-person. The study team will review the EMR and confirm eligibility.

# IRB Protocol for Human Subjects Research

The consent process will occur during face-to-face discussions with a study team member. The informed consent form will be read and reviewed by an approved member of the study team and all questions will be answered. The subject will be given ample time to ask questions and review the consent form before deciding about participation. All subjects will provide written informed consent before beginning any study activities and all will be given a copy of the signed consent form.

## 8.0 Diversity, Equity, and Inclusion

**8.1 Explain how the research plan (recruitment, study population, data collection, etc.) is equitable and represents the demographic makeup for the location in which the research will be conducted.**

The study will not favor or exclude any group of people outside the exclusionary criteria, which are implemented to prevent adverse events within the study to protect participants. Study staff will create an open and transparent environment to make sure participants are not only well-informed but feel safe when participating in the study.

**8.2 Describe whether non-English speaking subjects will be included in the study. If yes, please explain how your research team is prepared to meet the needs of the population. If not, please explain why non-English speakers will be excluded from the study population.**

Non-English-speaking subjects will not be included in the study. The study requires patient feedback on levels of pain through various paper surveys and verbal communication with tests in the lab. In order to maintain data clarity, subjects will be required to speak English as the current staff are not multi-lingual or have translators available.

**8.3 What methods will you use to collect demographic information from participants? If you will not collect demographic information, please explain why not.**

Demographic information will be obtained through a paper Medical History Questionnaire. All participants will complete a thorough questionnaire to collect demographic and medical history details, including age, sex, height, weight, duration of knee OA, current and past treatments for knee OA, comorbid conditions, and current medications.

## 9.0 Consenting Process:

**9.1 Indicate the informed consent process(es) and/or document(s) for the study. Check all that apply.**

# IRB Protocol for Human Subjects Research

Written Consent
 Informed Consent (ICF) – written or electronically signed form
 Parental Permission – written or electronically signed form
 Assent (participants under 18) – written or electronically signed form
 Combined ICF/PHI Authorization – written or electronically signed form
 Protected Health Information (PHI) Authorization – written or electronically signed
 Translated Consent/Assent – written or electronically signed form(s)
 Short Consent Form – written or electronically signed form (see guidance on Short Form process )
 Debriefing Script or Form – document used to properly inform subjects of the study's purpose when intentionally deceived

  

Oral/Online/Unsigned Consent
 Informed Consent – oral script/online/unsigned
 Parental Permission – oral script/online/unsigned
 Assent – oral script/online/unsigned
 Translated Consent/Assent – oral script/online/unsigned

  

Waivers of Informed Consent and/or PHI Authorization
 Waiver of Consent
 Full Waiver of PHI Authorization
 Partial Waiver of PHI for Screening Purposes

**9.2 Describe in detail the consent processes checked above, including any waiting period for subjects to sign the consent, steps to minimize the possibility of coercion or undue influence, and the language used by those obtaining consent.**

Subjects will have the option to participate in either the tDCS/MBM portion of the study alone or combined with the MRI scan portion at the start of the recruitment process. If the subject decides to participate in tDCS/MBM, an informed consent form will be given. There will be additional check box for the subject who decides to participate in MRI scan and additional signature will be collected.

Subjects will participate in the study only after they provide signed consent. Participation in this study is completely voluntary. All participants will be informed of the nature of the procedures and associated risks.

The consented subject will be screened for any contraindications to MRI and magnetic materials. The investigator or MRI Technologist will explain the MRI system and the scan that the subject will take part in. The subject will be asked to lie down on the scanner bed. Some part of the subjects' body may be covered or enclosed within an FDA or UA

# IRB Protocol for Human Subjects Research

HSPP approved MRI coil. The subject may be asked to interact with a peripheral system such as a button, joystick, or TV system before, during, or after the scan.

## Where will the original signed consent and PHI authorization documents be stored?

The original signed consent and PHI authorization documents will be stored in a locked office within a locked cabinet with the keys accessible only to the staff and PI.

### 9.3 Acknowledgement of consent form storage.

 I will store original signed consent and/or PHI authorization documents for at least 6 years past the time the study is concluded.
 For studies involving minors, I will store original signed consent and/or PHI authorization documents for at least 6 years after the youngest participant turns 18.
 Not applicable – I am not collecting signed documents.

# IRB Protocol for Human Subjects Research

## 10.0 Research and Data Collection Procedures:

### 10.1 Select the methods of data collection that will be used in this study (select all that apply):

 Anthropometric measures (e.g., height, weight, waist circumference, etc.)	 Participant observation
 Audio/video recording	 Screening data
 Benign interventions	 Self-health monitoring (e.g., pedometers, food diaries, etc.)
 Biological specimens – blood draws	 Surveys – paper
 Biological specimens – clinically discarded blood or specimens	 Surveys – internet (including online and email-based data collection)
 Biological specimens (urine/feces, tissue, saliva, skin, hair, nails, nasal swab)	 Surveys – telephone
 Clinical Data Warehouse (CDW)	 Randomization with control and experimental groups
 Cognitive or behavioral measures, including daily diaries	 Records – billing
 Data collected using other communication/electronic devices (e.g., cell phones, pagers, and texting devices)	 Records – educational
 Data previously collected for research purposes	 Records – employee
 Deception	 Records – lab, pathology and/or radiology results
 Instrumentation, equipment, or software not approved by the FDA	 Records – mental health
 Interviews – focus groups	 Records – substance abuse
 Interviews – in person	 Research imaging protocols
 Interviews – virtual/online	 Recombinant DNA
 Medical records review	 Social networking sites
 MRI/ultrasound with contrast	 Stem cells
 MRI/ultrasound without contrast	 Radiation Scans (X-Ray, CT Scans, etc.)
 Non-invasive instruments (e.g., external sensors applied to the body)	 Other activities or interventions – describe: Click or tap here to enter text.

# IRB Protocol for Human Subjects Research

## 10.2 Description of research procedures.

Participants who meet eligibility criteria and give informed consent will be randomly assigned at a ratio of 1:1:1:1 to one of the four groups: (a) active tDCS paired with active MBM (n=50), (b) sham tDCS paired with active MBM (n=50), (c) active tDCS paired with sham MBM (n=50), or (d) sham tDCS paired with sham MBM (n=50) using the order of entrance in the study and previous randomization list generated via SAS software. The randomization will balance the allocation of patients to the study arms with respect to distributions of age, race, and sex. tDCS with a constant current intensity of 2 mA will be applied for 20 minutes per session daily for 2 weeks (Monday to Friday) via the Soterix 1x1 tDCS mini-CT Stimulator device (Soterix Medical Inc., NY; 6.5 inches long, 3 inches wide, 0.7 inches thick) with headgear and 5x7 cm pre-saturated, single use, individually packed sponge electrodes. The FDA has ruled that the aforementioned tDCS stimulator is a “non-significant risk” device, a requirement for Investigational Device Exceptions. The sponge electrodes snap into the custom headgear, which is secured to the participant’s head for simple and fail-safe electrode preparation. This single-position headgear with clearly labeled sponge markers eliminates room for user error and helps conserve accurate and reproducible sponge placement. Participants can only administer a stimulation session via the Soterix 1x1 tDCS mini-CT Stimulator device after being provided a single-use unlock code by the research staff once proper contact quality is achieved (only the on/off button will be adjustable by the study participants; they will not be able to adjust the device settings). After the participant enters the unlock code, the screen on the device will show a timer that counts down the minutes until the end of the session. At 20 minutes, the device will turn off automatically, and study staff will instruct the participant to remove the headset and discard the sponges and to safely store all materials for the next session. For sham stimulation, the electrodes will be placed in the same positions as for active stimulation, but the stimulator will only deliver 2 mA current for 30 seconds. This sham stimulation method has been shown to be reliable and indistinguishable from active treatment. During each tDCS session, participants will practice MBM. The meditation intervention will be applied simultaneously with tDCS for 20 minutes per session daily for 2 weeks by a recorded meditation on a CD. Participants will be provided with a CD player and earphones. The recording will instruct participants to close their eyes, connect to the openness of one’s mind, and mindfully maintain and deepen the connection through breathing with more openness and awareness. The sham MBM intervention will be delivered via a CD player that will look identical in both active and sham MBM. The sham recording will instruct participants to relax and take deep breaths every 3 minutes without the specific mindfulness-based instructions (e.g., practicing mindful attention to the breath in a non-evaluative manner). All other aspects of the sham MBM intervention (e.g., body position, time spent listening to instructions, eyes closed) will match the active MBM.

Participants will perform self-administered tDCS and MBM at their home or private

# IRB Protocol for Human Subjects

## Research

room for two weeks (Mondays-Fridays) under real-time supervision by the research staff. The research staff will monitor participant for the accurate positioning of the headgear, optimized skin contact, proper usage of code to initiate the stimulation, and abide with the duration of the stimulation. Data will be collected by study staff across several points using equipment and resources available at [name] (PI's) laboratory at University of Arizona (see Table below). Participants will visit [name] lab three times, and each visit will take approximately 2 hours for tDCS/MBM study and additional 1 hour for MRI scan. Study team will not conduct a urine or blood pregnancy test.

	B		Week 1					Week 2						Monthly Follow-up		
			1	2	3	4	5†	6	7	8	9	10†		1-Mo	2-Mo	3-Mo
MRI		X											X			
MMSE	X															
Knee radiograph*	X															
Medical history questionnaire	X															
Clinical pain (NRS): primary outcome	X		X	X	X	X	X	X	X	X	X		X	X	X	
Osteoarthritis symptoms (WOMAC): secondary outcome	X						X					X		X	X	X
Pain-related cortical response(fNIRS): secondary outcome	X						X					X				
Descending pain modulation (CPM): secondary outcome	X						X					X				
Mindfulness (FMI): secondary outcome	X						X					X		X	X	X
COVID-related stress: secondary outcome	X						X					X		X	X	X
CESD: secondary outcome	X						X					X		X	X	X
PCS: secondary outcome	X						X					X		X	X	X
Patient satisfaction (CSQ-8): secondary outcome												X				

Note: B, Baseline; MRI, magnetic resonance imaging; MMSE, Mini-Mental Status Exam, NRS, Numeric Rating Scale; WOMAC, Western Ontario & McMaster Universities Osteoarthritis Index; fNIRS, functional near-infrared spectroscopy; CPM, conditioned pain modulation; FMI, Freiburg Mindfulness Inventory; CESD, Center for Epidemiologic Studies Depression Scale; PCS, Pain Catastrophizing Scale; CSQ, Client Satisfaction Questionnaire. The baseline visit will occur 3 to 7 days prior to the tDCS intervention.

\*Existing knee radiographs to determine OA severity using Kellgren-Lawrence scores.

# IRB Protocol for Human Subjects Research

†On days 5 and 10, tDCS paired with MBM will be delivered at [name] laboratory, followed by data collection of self-report measures (NRS, WOMAC, FMI, CSQ-8 [only day 10]), and immediately afterwards, the fNIRS and CPM will be collected.

- MRI. MRI will be completed within a week from the baseline visit and the last visit. Scans will be conducted at the Translational Bioimaging Resource (TBIR) located in UA. Only FDA-approved MRI devices will be used.
- MMSE. MMSE will be used to exclude people with diminished cognitive function (i.e., Mini-Mental Status Exam score  $\leq 23$ ).
- Kellgren-Lawrence Scores. Kellgren-Lawrence scores collected from existing patient x-rays will be conveyed from [name] to the research study team. If available, we will collect Kellgren-Lawrence Scores or x-rays directly from non-Banner affiliated participants. The scores will be used in the study to determine OA severity.
- Medical History Questionnaire. All participants will complete a thorough questionnaire to collect demographic and medical history details, including age, sex, height, weight, duration of knee OA, current and past treatments for knee OA, comorbid conditions, and current medications.
- Clinical pain intensity will be measured by asking participants to rate their average knee pain over the past 24 hours via NRS from 0 (no pain) to 100 (worst pain imaginable). Following the Initiative on Methods, Measurement, and Pain Assessment in Clinical Trials recommendations for clinical trials involving chronic pain, pain intensity changes assessed through an NRS will be our primary outcome measure for data analysis purposes.
- We will measure OA-related clinical symptoms using Western Ontario and McMaster Universities Osteoarthritis Index (WOMAC), which ranges from 0 to 96, with higher scores indicating worse OA pain-related symptoms.
- We will measure pain-related cortical response using a continuous-wave, multichannel fNIRS imaging system (LIGHTNIRS, Shimadzu, Kyoto, Japan). This instrument encompasses 8 light sources (each emitting laser light at 780, 805, and 830 nm) and 8 detectors connected to comfortable headgear using optical fibers. The illumination and detection optodes will be arranged in a geometrical layout that will cover the prefrontal and somatosensory cortex regions bilaterally, consistent with locations investigated in previous studies. Optical recordings will be collected during thermal and punctate pain stimulation. A temperature-controlled pain generator (Medoc TSA- II Neurosensory Analyzer) and nylon filament (Touch-Test Sensory Evaluators) will be used to produce thermal (maximum temperature of 50 Celsius degree) and punctate pain stimulation (maximum force of 300g). We will apply moderate intensity thermal and punctate stimuli for approximately 10-20 seconds, just enough time to feel the discomfort of the pain stimulation, to the most painful knee during multiple scanning runs, followed by an equivalent time period of no stimulation. In this

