## 10.3 Specify the total estimated time commitment for subject participation, and the estimated time commitment for each activity.

We expect that participants will be in this research study for four months. For a two-week period, participants will perform self-administered tDCS and MBM at their home or private room for eight days (Monday – Friday) of 20-minute supervised Zoom sessions. There will also be three lab visits lasting two hours each within those two weeks: once on the first day, once in the middle of the study, and once during the last day. Should they choose to participate, there will be two visits lasting one hour in the MRI facility, once before the first lab session and once after the last lab session. Finally, we will follow up with participants once a month for three months after the two-week period through phone survey for 20 minutes each or having the participant mail their paper survey answers to the office.

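### Is the first MRI placed before the baseline visit, and so before consent, by Section 10.3 of the protocol?

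*Combined protocol and SAP*

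**What the plan says.** All references are to the combined protocol and SAP.

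- **Section 10.2, notes under the schedule:** "MRI will be completed within a week from the baseline visit and the last visit". The same notes place the day 5 and day 10 sessions in the laboratory.
- **Section 10.2, schedule table and its note:** the first MRI mark sits in an unlabelled column between baseline and day 1, and the second in one between day 10 and the first monthly follow-up. Baseline is set 3 to 7 days before stimulation starts.
- **Section 10.2, text above the table:** three laboratory visits of about 2 hours, with a further hour for MRI.
- **Section 10.3:** "three lab visits lasting two hours each within those two weeks: once on the first day"; home sessions "at their home or private room for eight days"; and "two visits lasting one hour in the MRI facility, once before the first lab session and once after the last lab session".
- **Section 7.2:** people who contact the team give "informed consent in-person at a scheduled baseline visit". For everyone, "All subjects will provide written informed consent before beginning any study activities".
- **Section 9.2:** MRI consent is on the same form ("There will be additional check box for the subject who decides to participate in MRI scan and additional signature will be collected"), and "The consented subject will be screened for any contraindications to MRI and magnetic materials".
- **Section 12.2:** MRI suitability is checked at prospective enrolment, at enrolment and on the day of the scan.
- **Section 13.1:** up to $220 for the main protocol, and $100 for each of two MRI visits.

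**The concern.** Three texts deal with when the first scan happens, and they do not line up.

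1. **Order.** The table has baseline first and the scan second. Section 10.3 has the scan before the first lab session. If that session is the baseline visit, the scan comes before the consent taken there and before the cognitive screen that the table puts at baseline.
2. **Date.** Section 10.3 puts the first lab visit inside the two treatment weeks, on the first day. The table note puts baseline 3 to 7 days earlier.
3. **Number.** Section 10.2 can be read as adding an MRI hour to each of three visits, although only two scans are planned.

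At stake would be a scan without consent, a first scan that is not a clean pre-treatment measure for the imaging aim, or a variable interval between scans.

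**Working it through.** **Which visit is the first lab session?** Sessions: 8 at home (10.3) + 2 in the laboratory (days 5 and 10) = 10. The first of the three lab visits therefore carries no stimulation. Payment (13.1) gives the same count:

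- 10 sessions, 3 visits, 3 calls: 10 × $10 + 3 × $30 + 3 × $10 = $220, the stated maximum.
- A separate day 1 visit as well as baseline: 10 × $10 + 4 × $30 + 3 × $10 = $250, which does not match.

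The first lab session is most plausibly the baseline visit, although 10.3 never calls it that.

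**Timing under each reading.** Let D be the day of session 1, and take a Monday start (inferred from the Monday-to-Friday schedule). Day 10 is then D + 11. With a 7-day window, the second scan falls from D + 11 to D + 18. The interval between scans is the gap from first scan to session 1 plus 11 (minimum) or plus 18 (maximum).

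| Reading | Lab visits and pay | First scan to session 1 | First to second scan |
|---|---|---|---|
| Schedule table, baseline at D − 7 to D − 3 | 3, $220 | 0 to 7 days | 0 + 11 = 11 to 7 + 18 = 25 days |
| Order of 10.3, baseline dated by 10.2 | 3, $220 | 3 to 7 + 7 = 14 days | 3 + 11 = 14 to 14 + 18 = 32 days |
| Order of 10.3, first lab visit dated by 10.3 (D) | 3, $220 | 0 to 7 days | 11 to 25 days |
| 10.3 visit as an extra day 1 visit, scan after baseline | 4, $250 | 0 to 7 days | 11 to 25 days |

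Only the second row differs in timing, and it takes its order from one section and its date from another. Reading the window as under 7 days lowers the upper ends by at most 2 days.

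**Is the first scan always before treatment?** The window in the notes, read alone as after baseline, could run to D − 3 + 7 = D + 4. The table and 10.3 both place the first scan before session 1, so they agree on the point that matters for a pre-treatment scan.

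**Direction of the window.** One phrase covers both scans. For the last visit it can only mean afterwards, since the table and 10.3 both put the second scan later. The parallel reading for baseline is also afterwards, which matches the table and leaves 10.3 as the text out of step.

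**Consent.** The rows with the order of 10.3 and three visits put the scan ahead of a baseline consent. Against that stand the general rule in 7.2, the screening of consented subjects in 9.2 and the enrolment check in 12.2. A coordinator following those sections could not scan an unconsented person.

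**Number of scans.** Literal 10.2: 3 × (2 + 1) = 9 hours. Section 10.3: 3 × 2 + 2 × 1 = 8 hours. The table, 10.3 and 13.1 (2 × $100 = $200, not $300) all give two scans, so the extra hour in 10.2 is shorthand.

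**The case for a change.** The strongest case for acting is that no reading of 10.3 fits everything else. If the first lab session is baseline, the scan precedes the consent visit described in 7.2. If it is also on day 1, it contradicts the 3 to 7 days in the table note. If it is an extra visit, there are four lab visits and the $220 no longer adds up. This is the operative IRB text, the repair is a few words, and staff booking from 10.3 alone would use a different order from staff booking from the table.

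The inconsistency stands, and the date mismatch is its firmest part. The consequence does not. Staff do not book from a time estimate in isolation from the consent rule, and that rule is explicit. Section 7.2 ties consent to the baseline visit only for people who contact the team. It gives no date for orthopaedic referrals, so earlier consent is not excluded for them. The first and second complaints also strain against each other: the timing contrast needs baseline dated 3 to 7 days before treatment, while the date complaint needs the same visit on day 1.

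One caution applies to the table. The MRI column is unlabelled and the pain-rating row looks displaced, although the MRI row itself lines up with the day header.

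**Conclusion.** The concern does not hold as a point on the plan. Section 10.3 is loosely worded about the date of the first lab visit and its order relative to the first scan. That is a clerical slip which the rest of the protocol resolves: consent comes first, the first scan comes before treatment, and there are two scans.

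The most that can be attributed to it is a shift from 0 to 7 days to 3 to 14 days between first scan and session 1, and from 11 to 25 days to 14 to 32 days between scans. That rests on a mixed reading, a 7-day window and a Monday start. It would apply equally in all four arms, so it gives no bias between arms, and the documents do not use the interval as an analysis variable. The scan order and count concern an optional component with 40 planned completers out of 200 (20%). The date mismatch also touches the baseline pain, WOMAC, fNIRS and CPM measures, but equally across arms.

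Aligning the wording when the protocol is next revised would be good housekeeping. Nothing in the design, sample size, analysis or interpretation depends on it.
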